of 24 evaluable subjects will provide at least 90% power to exclude that LOXO-305 causes more than a 10-msec QTc effect at clinically relevant plasma levels, as shown by the upper bound of the 2-sided 90% confidence interval of the model-predicted QTc effect (placebo-corrected change from baseline ($\Delta\Delta$) QTc [$\Delta\Delta$ QTc]) at the observed geometric mean maximum observed plasma concentration (C_{max}) of LOXO-305 in the study. This power is estimated approximately using a paired t-test. The calculation assumes a 1-sided 5% significance level, a small underlying effect of LOXO-305 of 3 msec, and a standard deviation (SD) of the change from baseline (Δ) QTc (Δ QTc) of 8 msec for both LOXO-305 and placebo.

Main Criteria for Inclusion

Male subjects, and female subjects of non-childbearing potential must meet the following criteria:

- Between 18 and 55 years of age, inclusive, at Screening
- Within body mass index (BMI) range 18.0 to 32.0 kg/m², inclusive at Screening
- In good general health, based on medical history, physical examination findings, vital signs, standard safety 12-lead ECG, or clinical laboratory evaluations at Screening and/or Check-in (Day -1), as determined by the Investigator (or designee)

Investigational Medicinal Products, Dose, and Mode of Administration

Subject will receive each of the following treatments once throughout the study:

Treatment A:

- A single oral dose of 900 mg LOXO-305 (36 × 25-mg tablets, over-encapsulated [9 capsules]), following a fast of at least 8 hours prior to and 6 hours after dosing.

Treatment B:

- A single oral dose of placebo to match 900 mg LOXO-305 (9 capsules), following a fast of at least 8 hours prior to and 6 hours after dosing.

Treatment C:

- A single oral dose of 400 mg moxifloxacin (1 × 400 mg tablet), following a fast of at least 8 hours prior to and 6 hours after dosing.

Duration of Subject Participation in the Study:

Planned Enrollment/Screening Duration: Approximately 28 days (Days -29 to -2).

Length of CRU Confinement: Up to 34 days (Days -1 to 33).

Planned Study Conduct Duration: Approximately 71 days (Screening through follow-up call).

Criteria for Evaluation:

Pharmacokinetics:

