8. SAMPLE SIZE AND DATA ANALYSIS

8.1. Determination of Sample Size

A total of up to 30 subjects (5 subjects per treatment sequence) will be enrolled to ensure at least 24 evaluable subjects completed all three treatment periods of the study. A sample size of 24 evaluable subjects will provide at least 90% power to exclude that LOXO-305 causes more than a 10-msec QTc effect at clinically relevant plasma levels, as shown by the upper bound of the 2-sided 90% CI of the model-predicted QTc effect ($\Delta\Delta QTc$) at the observed geometric mean C_{max} of LOXO-305 in the study. This power is estimated approximately using a paired t-test. The calculation assumes a 1-sided 5% significance level, a small underlying effect of LOXO-305 of 3 msec, and a standard deviation (SD) of the ΔQTc of 8 msec for both LOXO-305 and placebo. The concentration-QTc analysis method is supported by Darpo et al¹⁴ and Ferber et al¹⁵, and is consistent with the experiences from 25 recent TQT studies.

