6.2 Concentration-QTc Analysis (Primary Analysis)

The relationship between LOXO-305 plasma concentrations and change-from-baseline QTc ($\Delta QTcF$, or ΔQTc corrected with the HR correction method chosen as primary if a substantial HR effect is observed) be quantified using a linear mixed-effects modeling approach. The model will include ΔQTc as the dependent variable, LOXO-305 plasma concentrations as the explanatory variate (0 for placebo), centered baseline QTc (i.e., baseline QTc for individual subject minus the population mean baseline QTc for all subjects in the same treatment period) as an additional covariate, treatment (active = 1 or placebo = 0), time (i.e., nominal post-dose time point) as fixed effects, and random effects on the intercept and slope per subject¹. In addition, if there are significant concentrations of LOXO-305 metabolites, their concentrations/QTc relationship may be explored (exploratory metabolite profiling has shown that unchanged LOXO-305 is the major drug-related component in human plasma). In all calculations, zero will be substituted for concentrations below the quantification limit of the assay and for concentrations from subjects who received placebo.

An unstructured covariance matrix will be specified for the random effects. If convergence cannot be achieved even after appropriate rescaling of the concentrations, the random effect on the slope and intercept will be dropped, in this order, until convergence is achieved. The degrees of freedom of estimates will be determined by the Kenward-Roger method. From the model, the slope (i.e., the regression parameter for LOXO-305 concentrations) and the treatment effect-specific intercept (defined as the difference between active and placebo) will be estimated together with the 2-sided 90% CI. The estimates for the time effect will be reported with degrees of freedom and SE.

The geometric mean of the individual C_{max} values for subjects in the active dose group will be determined. The predicted effect and its 2-sided 90% CI for $\Delta\Delta QTc$ (i.e., slope estimate \times concentration + treatment effect-specific intercept) at this geometric mean C_{max} of LOXO-305 will be obtained. If the upper bound of the 2-sided 90% CI of the predicted effect of $\Delta\Delta QTc$ at clinically relevant plasma levels of LOXO-305 is below 10 ms, it will be concluded that LOXO-305 does not cause clinically relevant QTc prolongation within the observed plasma concentration ranges.

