To evaluate the adequacy of model fit with respect to the assumption of linearity, the observed ΔQTc values adjusted by population time effect estimated from the model will be used. These individual placebo-adjusted $\Delta QTc_{i,k}$ ($\Delta\Delta QTc_{i,k}$) values equal the observed individual $\Delta QTc_{i,k}$ for subject i administered with active drug or placebo at time point k minus the estimated population mean placebo effect at time point k (i.e., time effect). A quantile plot, i.e. plot of the quantiles (deciles) of observed drug concentrations and the mean placebo-adjusted ΔQTc ($\Delta\Delta QTc$) and 90% CI at the median concentration within each decile will be given. The regression line presenting the model-predicted $\Delta\Delta QTc$ (as described by Tornøe et al²) will be added to evaluate the fit of a linear model and visualize the concentration-response relationship. Additional exploratory analyses (via graphical displays and/or model fitting) will include assessing for a delayed effect (hysteresis, [Section 6.2.1](#)) and the justification for the choice of the pharmacodynamic model (linear versus nonlinear, [Section 6.2.2](#)) as follows.

The SAS code for the concentration-QTc analysis using the full model is as follows.

```
PROC MIXED DATA=PKPD method=reml;
CLASS SUBJID TIME;
MODEL DQTc=TRT CONC TIME CBASE/ solution cl noint alpha=0.1 alphap=0.1 COVB DDFM=KR;
RANDOM INT CONC /type=UN SUBJECT=SUBJID s;
RUN;
```

Where PKPD = PK/QTc population, SUBJID = subject number, TRT = treatment (active = 1 or placebo = 0), TIME = nominal post-dose time point, CONC = time-matched plasma concentration of LOXO-305 (0 for placebo), CBASE = centered baseline QTcF, and DQTc = Δ QTcF.

Note: ESTIMATE statements will be included for the prediction of the effect in the active dose group.

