6.8 Determination of Sample Size

A total of up to 30 subjects (5 subjects per treatment sequence) will be enrolled to ensure at least 24 evaluable subjects completed all three treatment periods of the study. A sample size of 24 evaluable subjects will provide at least 90% power to exclude that LOXO-305 causes more than a 10-ms QTc effect at clinically relevant plasma levels, as shown by the upper bound of the 2-sided 90% CI of the model-predicted QTc effect ($\Delta\Delta QTc$) at the observed geometric mean Cmax of LOXO-305 in the study. This power is estimated approximately using a paired t-test. The calculation assumes a 1-sided 5% significance level, a small underlying effect of LOXO-305 of 3 ms, and a standard deviation (SD) of the ΔQTc of 8 ms for both LOXO-305 and placebo. The concentration-QTc analysis method is supported by Darpo et al⁵ and Ferber et al⁶, and is consistent with the experiences from 25 recent TQT studies.

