6.8.1 Determination of Sample Size for Assay Sensitivity

To demonstrate assay sensitivity with concentration-QTc analysis, it has to be shown that the $\Delta\Delta QTc$ of a single dose of 400 mg moxifloxacin exceeds 5 ms (ie, the lower bound of the 2-sided 90% CI of the predicted QTc effect [$\Delta\Delta QTc$] should exceed 5 ms). In a similarly designed, recent crossover study with 24 healthy subjects (on-file data, ERT), the standard error (SE) for the prediction of the QT effect of moxifloxacin based on the concentration-QTc analysis was 1.24 ms. The within-subject SD of $\Delta QTcF$ in the referred study was 5.4 ms based on the by-timepoint analysis. If the effect of moxifloxacin is assumed to be 10 ms, the SE of 1.24 ms corresponds to an effect size of $(10-5)/(1.24 \times \sqrt{24}) = 0.82$, where the effect size is the effect assumed under the alternative hypothesis divided by the SD of the test variable. This value should be compared to the effect size of 0.62 required to guarantee a power of at least 90% in a paired t-test situation with a sample size of 24 evaluable subjects. In other words, based on this calculation, a power of at least 90% for 24 evaluable subjects will be obtained as long as the variability of the ΔQTc , as measured by its within-subject SD, does not exceed 7.1 ms (ie, 132% [= 0.82/0.62] of the 5.4 ms observed in the referred study assuming the ratio of effective sizes is

consistent with inverse ratio of within-subject SD). The number also agrees with recent recommendations of the FDA, which propose at least 20 subjects⁷.

7 References

3. Cleveland WS. Robust locally weighted regression and smoothing scatterplots. *J Am Stat Assoc*. 1979;74(368):829-836.

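### The primary rule tests the 10 ms limit at the geometric mean Cmax but draws its conclusion for the whole observed concentration range

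*SAP*

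**What the plan says.** SAP 6.2 and Protocol 8.3.4 set out the same rule. The predicted ΔΔQTc (slope times concentration plus the treatment-specific intercept) and its 2-sided 90% CI are computed at the geometric mean of the individual Cmax values. The decision sentence then asks whether the upper bound "at clinically relevant plasma levels of LOXO-305 is below 10 ms". If so, "it will be concluded that LOXO-305 does not cause clinically relevant QTc prolongation within the observed plasma concentration ranges".

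The decision sentence gives no figure for the clinically relevant levels. Protocol 8.1 supplies the meaning. It describes exclusion of a 10 ms effect "at clinically relevant plasma levels, as shown by the upper bound of the 2-sided 90% CI of the model-predicted QTc effect" and places that bound at the observed geometric mean Cmax. SAP 6.8 repeats this ("at the observed geometric mean Cmax of LOXO-305 in the study"), and the Protocol synopsis agrees.

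The planned outputs match that reading: Table 14.1.12.1 and Figure 14.2.11.1 give the prediction at the geometric mean peak. Figures 14.2.9.1 and 14.2.10.1 show the model prediction with its 90% CI across observed concentrations, but no rule refers to them.

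**The concern.** One rule carries three concentration scopes: the point that is computed, an undefined clinically relevant level, and the full observed range. The evidence comes from the first and the claim is made for the last.

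The geometric mean Cmax lies inside the observed range, not at its upper end. With a positive slope, a bound below 10 ms at that point does not imply a bound below 10 ms at higher observed concentrations. A trial could therefore report no clinically relevant prolongation over its observed range while its own figures show an upper bound of 10 ms or more in part of that range. The claim at stake concerns the upper tail of exposure.

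**Working it through.** **Inputs.** From SAP 6.8: margin 10 ms, one-sided 5%, true effect 3 ms, SD of ΔQTc 8 ms on each treatment, n = 24; "This power is estimated approximately using a paired t-test". From SAP 6.8.1, as an analogue only: the SE for "the prediction of the QT effect of moxifloxacin based on the concentration-QTc analysis was 1.24 ms". From Protocol Table 1 (patients at steady state): Cmax CV from 11.0% (25 mg, 5 patients) to 47.7% (200 mg, 99 patients). The healthy-subject CV is not given, so this range is an assumption.

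**1. The plan's own figure.** SE = √2 × 8/√24 = 2.309 ms, taking zero within-subject correlation. t(0.95, 23 df) = 1.714. The noncentrality is (10 − 3)/2.309 = 3.03, and the noncentral-t power is 90.2%. The stated power of at least 90% reproduces, and it applies at the geometric mean Cmax.

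**2. Where the expected bound crosses 10 ms.** Assume a linear effect, zero intercept, and an SE proportional to concentration. The bound at R times the geometric mean Cmax is then R × U, where U is the bound at the geometric mean Cmax.

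| True effect | SE at GM Cmax | U = effect + 1.714 × SE | Crossing, 10/U |
|---|---|---|---|
| 3 ms | 2.309 | 6.96 ms | 1.44 |
| 3 ms | 1.24 | 5.13 ms | 1.95 |
| 0 ms | 2.309 | 3.96 ms | 2.53 |
| 0 ms | 1.24 | 2.13 ms | 4.71 |

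If the SE is constant instead, the first row crosses at (10 − 3.96)/3 = 2.01.

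**3. How far observed peaks extend.** For lognormal Cmax, σ = √ln(1 + CV²). For CVs of 11.0, 19.2, 26.6 and 47.7%, σ = 0.110, 0.190, 0.261 and 0.453. The highest of 24 values then averages 1.24, 1.45, 1.68 and 2.47 times the sample geometric mean.

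**4. Share of passing trials whose bound is at least 10 ms at the highest Cmax.** There were 400,000 simulated trials per cell. The estimate is N(effect, SE), the estimated SE is SE × √(χ²₂₃/23), and a trial passes if U < 10. The table gives the share of passing trials with R × U ≥ 10, where R is that trial's highest Cmax divided by its geometric mean.

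| Effect, SE | CV 11.0% | 19.2% | 26.6% | 47.7% |
|---|---|---|---|---|
| 3 ms, 2.309 | 24% | 44% | 60% | 84% |
| 3 ms, 1.24 | 1% | 10% | 26% | 71% |
| 0 ms, 2.309 | 4% | 10% | 19% | 45% |
| 0 ms, 1.24 | 0% | 0.04% | 0.4% | 8% |

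**5. Sensitivity at 3 ms, lowest to highest CV.**

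| Assumption | SE 2.309 | SE 1.24 |
|---|---|---|
| SE constant in concentration: estimate × R + half-width | 12% to 53% | 0.5% to 41% |
| Fixed 2 ms intercept: 2 + (U − 2) × R | 18% to 70% | 0.6% to 42% |
| Both together | 7% to 31% | 0.2% to 13% |

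**6. When the broad conclusion would be false.** Suppose the true effect reaches 10 ms at R times the geometric mean Cmax and is proportional to concentration. The effect at the tested point is then 10/R, and the rule passes with noncentrality (10 − 10/R)/2.309.
- R = 1.5: true effect 6.67 ms at the tested point, noncentrality 1.44, pass probability 40%.
- R = 2: true effect 5 ms, noncentrality 2.17, pass probability 68%.

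**The case against.** The strongest reply is that the percentages in step 4 count failure to exclude, not wrong conclusions. This stands. In the 3 ms scenario the true mean effect at the highest Cmax averages 3.7 ms (CV 11.0%) to 7.4 ms (CV 47.7%). It reaches 10 ms in none of the passing trials at the three lower CVs and in about 8% at 47.7%. In most of these trials the broad statement would be true but unproven. The 40% and 68% in step 6 do concern false conclusions, but they need a larger true effect than the plan assumes.

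The main table also uses the less favourable assumptions. The planned model has a treatment-specific intercept, the SE need not grow in proportion to concentration, and an SE of 2.309 ms ignores within-subject correlation. The milder rows in step 5 matter for that reason. The highest of 24 peaks is one extreme observation, and the statement that about half lie above the geometric mean concerns peaks, not all samples.

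The tested exposure is already intended to be about twice the therapeutic steady-state Cmax (Protocol 3.3.1), and a crossing would be visible in the planned figures. Both points are correct. They support a claim up to the tested concentration, but not a prespecified conclusion beyond it.

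Finally, the decision sentence does not literally say that only the geometric mean Cmax is tested. That reading rests on the preceding sentence, the sample-size text and the output list, which all agree. Reading the phrase as therapeutic levels would widen the gap to the stated conclusion.

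**Conclusion.** The concern holds. The prespecified conclusion covers more than the prespecified test supports, in the same way in both documents. That follows from the wording and from a positive slope; it does not depend on the simulations.

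The practical size depends on the scenario. With a 3 ms effect, the share of passing trials that cannot exclude 10 ms at their highest Cmax runs from 24% to 84% with the plan's approximate SE, and from 1% to 71% with the moxifloxacin model SE. It is lower with an intercept or a constant SE, and at most 8% with no true effect and the smaller SE. These figures assume linearity, lognormal Cmax and CVs borrowed from patients. They are not an expected error rate.

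The primary estimate, the margin and the 90% power at the geometric mean Cmax are unaffected. This should be fixed because the overreach is in the sentence that states the trial's main conclusion.

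**What to change.** In SAP 6.2 and Protocol 8.3.4:

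- Replace the undefined concentration phrase in the decision sentence with the observed geometric mean Cmax, and keep that as the primary test.
- Reword the conclusion along these lines: *an effect of 10 ms or more is excluded at the geometric mean Cmax, and at those observed concentrations where the upper limit of the two-sided 90% interval for predicted ΔΔQTc is also under 10 ms*.
- Evaluate the bound over the whole observed range and report both ends of the passing interval. Because the model has a treatment-specific intercept, the bound is convex in concentration for a fixed t value. The passing concentrations therefore form one interval, which need not start at the lowest concentration.
- As an addition on which the fix does not depend, report the upper end as a multiple of the 200 mg QD steady-state geometric mean Cmax. The reference must first be reconciled: Table 1 prints 5770 ng/mL, while the 12860 ng/mL target described as 2-fold implies 12860/2 = 6430 ng/mL (12860/5770 = 2.23).

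The cost is one reworded rule in the SAP and a matching protocol clarification. The planned PROC MIXED call already requests COVB, and "ESTIMATE statements will be included for the prediction of the effect in the active dose group", so one or two further ESTIMATE statements suffice. Data, model, margin and sample size do not change. The price is a narrower claim.

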3.2. Discussion of Study Design

The study design includes the use of a placebo, a supratherapeutic dose of LOXO-305 to mimic the exposure in healthy subjects that may occur in the target population under the most extreme circumstances and to assess the effect on cardiac repolarization and a positive control, moxifloxacin. Modeling the C-QT relationship observed during this study will characterize the QT prolongation effect over the observed drug concentration of a supratherapeutic dose of LOXO-305 to assess the drug cardiac effect at therapeutic doses.

A randomized crossover design has been selected to minimize assignment bias and to allow each subject to serve as his or her own control, which improves the precision of the estimated treatment differences as well as decreasing the overall number of subjects needed for the study. It will be a partially double-blind study with respect to LOXO-305 and LOXO-305 matched placebo because blinding eliminates confounding by concomitant interventions and biased safety findings, thus eliminating the possibility that the observed effects of intervention are because of differential use of other treatments or biased expectations regarding safety.

Placebo has been chosen as the control treatment to assess whether any observed effects are treatment-related or simply reflect the study conditions. Moxifloxacin as a single 400-mg dose is a standard positive control to be used in QT studies to assess assay sensitivity. This product has been shown to produce a peak QTc prolongation ranging from 10 to 15 msec in crossover design studies,^{12,13} with a mean QTc prolongation of about 5 msec. Hence, moxifloxacin-induced changes in ventricular repolarization, when compared to the placebo treatment in healthy subjects, will be used to evaluate assay sensitivity.^{13,11}

The sampling scheme is expected to adequately characterize the LOXO-305 exposure-response relationship including hysteresis and late effects and diurnal variability, and the washout period of at least 10 days between each treatment period is considered sufficient to prevent carryover effects of the treatments.

Conducting the study in healthy adult subjects mitigates the potential confounding effects of the disease state and concomitant medications.

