8.3.4. Concentration-QTc Analysis (Primary Analysis)

The relationship between LOXO-305 plasma concentrations and change from baseline QTc ($\Delta QTcF$ or ΔQTc corrected with the HR correction method chosen as primary if a substantial HR effect is observed) will be quantified using a linear mixed-effects modeling approach. The model will include ΔQTc as the dependent variable, LOXO-305 plasma concentrations as the explanatory variate (0 for placebo), centered baseline QTc (ie, baseline QTcF for individual subject minus the population mean baseline QTc for all subjects in the same treatment period) as an additional covariate, treatment (active = 1 or placebo = 0) and time (ie, nominal postdose timepoint) as fixed effects, and random effects on the intercept and slope per subject.¹⁸ In addition, if there are significant concentrations of LOXO-305 metabolites, their concentrations/QTc relationship may be explored (exploratory metabolite profiling has shown that unchanged LOXO-305 is the major drug-related component in human plasma).

The degrees of freedom of estimates will be determined by the Kenward-Roger method. From the model, the slope (ie, the regression parameter for LOXO-305 concentrations) and the treatment effect-specific intercept (defined as the difference between active and placebo)

will be estimated together with the 2-sided 90% CI. The estimates for the time effect will be reported with degrees of freedom and SE.

The geometric mean of the individual C_{max} values for subjects in the active dose group will be determined. The predicted effect and its 2-sided 90% CI for $\Delta\Delta QTc$ (ie, slope estimate \times concentration + treatment effect-specific intercept) at this geometric mean C_{max} of LOXO-305 will be obtained. If the upper bound of the 2-sided 90% CI of the predicted effect of $\Delta\Delta QTc$ at clinically relevant plasma levels of LOXO-305 is below 10 msec, it will be concluded that LOXO-305 does not cause clinically relevant QTc prolongation within the observed plasma concentration ranges.

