4.2.2 Secondary Objectives

- To assess the effect of a single supratherapeutic dose exposure of LOXO-305 on other ECG parameters (HR, PR, and QRS interval) and on T-wave morphology changes compared with placebo in healthy subjects.

- To demonstrate sensitivity of the study to detect a small QTc effect using 400 mg oral moxifloxacin as a positive control in healthy subjects.
- To evaluate the PK of a single supratherapeutic dose of LOXO-305 in healthy subjects.
- To evaluate the safety and tolerability of a single supratherapeutic dose of LOXO-305 in healthy subjects.

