6.3 Assay Sensitivity

The analysis to show assay sensitivity will be based on the concentration-QTc analysis of the effect on ΔQTc of 400 mg oral moxifloxacin using a similar model as for the primary analysis. That is, the relationship between moxifloxacin plasma concentration and ΔQTc will be investigated by linear mixed-effects modeling. The model will include ΔQTc as the dependent variable, moxifloxacin plasma concentration as the explanatory variable (0 for placebo), centered baseline QTc (i.e., baseline QTc for individual subject minus the population mean baseline QTc for all subjects in the same treatment period) as an additional covariate, study treatment (moxifloxacin = 1 or placebo = 0) and time (i.e., post-dose time point) as fixed effects, and a random intercept and slope per subject (Garnett et al¹). The geometric mean of the individual C_{max} values for subjects receiving the single dose of 400 mg moxifloxacin will be determined. The predicted effect and its 2-sided 90% CI for $\Delta\Delta QTc$ (i.e., slope estimate \times concentration + treatment effect-specific intercept) at this geometric mean C_{max} will be obtained.

If the slope of the moxifloxacin plasma concentration/ ΔQTc relationship is statistically significant at the 10% level in a 2-sided test and the lower bound of the 2-sided 90% CI of the predicted QT effect at the observed geometric C_{max} of the 400 mg dose is above 5 ms, assay sensitivity will be deemed to have been demonstrated.

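### The primary rule lets a negative QTc conclusion stand on the 10 ms bound alone; neither document says what follows for LOXO-305 if the moxifloxacin control fails

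*SAP*

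**What the plan says.** **Primary rule.** SAP 6.2 predicts ΔΔQTc at the geometric mean Cmax of LOXO-305. If the upper bound of its 2-sided 90% CI is below 10 ms, "it will be concluded that LOXO-305 does not cause clinically relevant QTc prolongation within the observed plasma concentration ranges". Protocol 8.3.4 has the same rule: if the bound "is below 10 msec, it will be concluded that LOXO-305 does not cause clinically relevant QTc prolongation within the observed plasma concentration ranges". Neither mentions moxifloxacin.

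**Assay sensitivity rule.** SAP 6.3 has two parts. The moxifloxacin slope "relationship is statistically significant at the 10% level in a 2-sided test", and the lower 90% bound at its geometric mean Cmax "is above 5 ms, assay sensitivity will be deemed to have been demonstrated". Protocol 3.3.2 and 8.3.5 give the same two criteria. All three sections stop at that label.

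**Role of the control.** Protocol 3.2 explains why it is there: "Moxifloxacin as a single 400-mg dose is a standard positive control to be used in QT studies to assess assay sensitivity". It is a secondary objective (SAP 4.2.2, Protocol 2.1.2): "To demonstrate sensitivity of the study to detect a small QTc effect using 400 mg oral moxifloxacin as a positive control in healthy subjects". It has its own sample-size section (SAP 6.8.1, Protocol 8.1.1) and its own output (for example SAP Tables 14.1.11.2 and 14.1.12.2). No section says how the LOXO-305 result is read if the control fails.

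**The concern.** The primary test is passed by a small measured effect. Anything that shrinks measured QTc changes across the whole study therefore moves LOXO-305 towards a pass. A positive control is included to detect that loss of sensitivity, and each subject gives one of three periods to it. Its result has to bear on the conclusion for that to be worthwhile.

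The primary sentence is mandatory in tone and has one condition. If moxifloxacin failed and the LOXO-305 bound were below 10 ms, the prespecified conclusion would still be negative. Any qualification would have to be added after the LOXO-305 result was known, and against the plan's own wording.

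**Working it through.** **Inputs from the plan** (SAP 6.8 and 6.8.1; Protocol 8.1 and 8.1.1): 24 evaluable subjects; one-sided 5%; margin 10 ms; assumed LOXO-305 effect 3 ms; SD of ΔQTc 8 ms on each of LOXO-305 and placebo; paired t-test. For moxifloxacin: effect 10 ms, threshold 5 ms, prediction SE 1.24 ms at a within-subject SD of 5.4 ms, SD limit 7.1 ms.

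**Method.** Power is P(T > 1.714), where T is noncentral t with 23 df and noncentrality (distance from threshold)/SE.

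**Step 1. Reproduce the plan's figures.**
- Primary: SD of the paired difference = 8 × √2 = 11.31 ms (zero within-subject correlation assumed). SE = 11.31/√24 = 2.31 ms. Noncentrality = (10 − 3)/2.31 = 3.03. Power = 90.2%, against a stated minimum of 90%.
- Moxifloxacin: effect size = 5/(1.24 × √24) = 0.82, as stated. The effect size needed for 90% power is 0.616 (stated 0.62). SD limit = 5.4 × 0.82/0.62 = 7.1 ms, as stated.
- Moxifloxacin pass rate on the 5 ms bound: 98.8% at SE 1.24. At the SD limit, SE = 1.24 × 7.1/5.4 = 1.63 and the pass rate is 90.8%.

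The sample-size arithmetic is sound.

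**Step 2. What the missing link could allow (hypothetical).** Assume a true effect of 10 ms for both drugs. Assume the study records only a fraction f of each effect, with the same f for both and unchanged noise. The fractions are my assumption and appear nowhere in the documents. LOXO-305 passes with noncentrality (10 − 10f)/2.31. Moxifloxacin passes with noncentrality (10f − 5)/SE. Ranges run from SE 1.63 to SE 1.24.

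| f | Negative, current rule | Moxifloxacin passes | Negative with both required (independent) | Ceiling under any dependence |
|---|---|---|---|---|
| 1 | 5.0% | 91–99% | 4.5–4.9% | 5.0% |
| 0.75 | 27.6% | 44–62% | 12–17% | 27.6% |
| 0.6 | 51.4% | 15–19% | 8–10% | 15–19% |
| 0.5 | 67.6% | 5% | 3% | 5% |

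The ceiling is the smaller of the two pass rates. It is needed because both tests share the placebo data.

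**Step 3. Cost in power when nothing is wrong** (LOXO-305 effect 3 ms, moxifloxacin 10 ms). Joint power = 0.902 × moxifloxacin pass rate if independent. The lower bound under any dependence is the sum of the two rates minus 1.
- SE 1.24: 0.902 × 0.988 = 89%; lower bound 89%.
- SE 1.63 (SD 7.1 ms): 0.902 × 0.908 = 82%; lower bound 81%.
- SE 1.24 × 8/5.4 = 1.84 (SD 8 ms, as in the primary calculation): pass rate 84.0%; 0.902 × 0.840 = 76%; lower bound 74%.

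These cover the 5 ms bound only. The slope test is not included.

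**The case against.** The strongest reply is that the plan is silent rather than wrong. A reader might infer that it instructs the sponsor to disregard moxifloxacin, and no section says so. The control is a named objective with a prespecified criterion, its own power calculation and its own tables, so a failure would appear in the same report. That stands as a limit on the wording. It does not supply the missing consequence, because the only rule stated for LOXO-305 still returns a negative.

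A reader might also infer that moxifloxacin is the plan's only protection against lost sensitivity. The documents do not support that. There is blinded central reading with beat-level quality control (Protocol 7.2.1), supervised dosing with mouth checks (Protocol 5.5), a by-time-point analysis that uses no concentrations, and hysteresis and residual checks (SAP 6.2.1, 6.2.2, 6.4). Nor does the control catch everything: an error confined to the LOXO-305 period or its PK data could leave moxifloxacin passing.

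The illustration depends on a common attenuation factor that the documents do not give. Under milder attenuation the gain is smaller: at f = 0.8 with SE 1.24, 21% falls only to 16%. Under the plan's own assumptions moxifloxacin fails in about 1% of studies. All of this stands.

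The cost can also be put higher. Giving moxifloxacin the primary's paired SD of 11.31 ms yields a 68% pass rate and joint power near 61%. That replaces the model-based SE that the plan itself uses for moxifloxacin, so I treat it as an extreme, but it shows that the cost depends on the SD.

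**Conclusion.** The point holds as a gap in the decision rule. The negative conclusion rests solely on the 10 ms bound, and nothing ties it to assay sensitivity or says what a failed control means. Followed exactly, the plan gives a negative conclusion from a study that has not shown it can detect a small effect.

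It would go too far to say that the plan's 5% error rate is wrong. With unattenuated effects the rule errs in 5.0% of studies at a true effect of 10 ms. The rates of 28%, 51% and 68% arise only under the hypothetical common attenuation. Requiring assay sensitivity can never raise the false-negative rate, because it only adds a condition. It helps most under severe loss of sensitivity. At f = 0.75 the gain depends on how the two tests are correlated.

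This should be changed before analysis. The estimates, intervals and sample-size arithmetic are not in question.

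**What to change.** In SAP 6.2 and Protocol 8.3.4, make the negative conclusion require both an upper bound below 10 ms and assay sensitivity demonstrated under SAP 6.3 (Protocol 8.3.5). Add a sentence saying that an upper bound below 10 ms without assay sensitivity is inconclusive for absence of a QTc effect. Say also that a finding of prolongation does not depend on assay sensitivity.

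The cost is two or three sentences in each document. Alpha, enrolment and data collection do not change. The price is a lower chance of a clean negative conclusion, so SAP 6.8 and Protocol 8.1 should report joint power across the range in Step 3, with the independence assumption named. The sponsor should add the slope criterion to that calculation and then judge whether 24 evaluable subjects remain enough.
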